10.2 Handling of Multiplicity

No multiplicity adjustment is needed for this study because there is no hypothesis testing for the primary and secondary efficacy endpoints.

10.3 Primary Efficacy Analysis

The primary efficacy endpoint is SVR₁₂ (HCV RNA < LLOQ 12 weeks after the last actual dose of study drug) in the ITT population. The number and percentage of subjects achieving SVR₁₂ will be summarized by GT (GT5 and GT6) across treatment arms. The number and percentage of subjects achieving SVR₁₂ will be calculated along with a two-sided 95% CI using the normal approximation to the binomial distribution, unless the number of SVR₁₂ non-responders is less than 5, where the Wilson's score method¹ will be used to calculate the CI instead.

A summary of reasons for SVR₁₂ non-response (e.g., on-treatment virologic failure, relapse, other) will be provided. A listing of subjects who do not achieve SVR₁₂ by reason for non-response will also be provided.

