1.2 Synopsis

AbbVie Inc.	Protocol Number: M16-126
Name of Study Drug: Glecaprevir, Pibrentasvir	Phase of Development: 3b
Name of Active Ingredient: Glecaprevir Pibrentasvir	Date of Protocol Synopsis: 28 July 2017
Protocol Title: A Multicenter, Open-Label Study to Evaluate the Efficacy and Safety of Glecaprevir (GLE)/Pibrentasvir (PIB) in Adults with Chronic Hepatitis C Virus (HCV) Genotype 5 or 6 Infection	
Objectives: 
 The primary objectives of this study are to assess the efficacy (by evaluating the percentage of subjects achieving SVR₁₂) and safety of glecaprevir/pibrentasvir in adults with chronic hepatitis C virus (HCV) genotype (GT) 5 or 6 infection with or without compensated cirrhosis. The efficacy of glecaprevir/pibrentasvir will be assessed by genotypes across treatment durations (or cirrhosis status) and the safety of glecaprevir/pibrentasvir will be assessed by treatment duration (or cirrhosis status) across genotypes. The secondary objectives are to assess efficacy of glecaprevir/pibrentasvir by hepatitis C virus (HCV) genotype (GT) 5 or 6 infection across treatment duration (or cirrhosis status) by evaluating the percentages of subjects with HCV on-treatment virologic failure and HCV virologic relapse across treatment durations (or cirrhosis status). 
Additional objectives are to assess pharmacokinetics and emergence and persistence of viral variants in these treatment regimens.
	
Investigators: Multicenter	
Study Sites: Approximately 26	
Study Population: Chronic HCV GT5 or 6-infected male and female adults aged 18 years or older, without cirrhosis or with compensated cirrhosis, who are either HCV treatment-naïve (i.e., has never received a single dose of any approved or investigational anti-HCV medication) or treatment experienced (i.e., has failed prior interferon [IFN] or pegylated interferon [pegIFN] with or without ribavirin [RBV], or sofosbuvir [SOF] plus RBV with or without pegIFN therapy).	
Number of Subjects to be Enrolled: Approximately 80 subjects	

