
Criteria for Evaluation:
 
Efficacy: Plasma HCV RNA (IU/mL) will be assessed at each Treatment and Post-Treatment Visit.
 
Safety: Safety and tolerability will be assessed by monitoring adverse events, physical examinations, clinical laboratory tests, and vital signs.
 
Patient Reported Outcomes (PROs): The Short Form 36 Version 2 Health Status Survey (SF-36v2) will be used to assess the functional health and well-being of subjects. The Work Productivity and Activity Impairment Questionnaire: Hepatitis C (WPAI: Hepatitis C) will assess work and activity impairment due to HCV.
 
Pharmacokinetic: Individual plasma concentrations of glecaprevir and pibrentasvir will be tabulated and summarized.
 
Resistance: The following information will be tabulated and summarized: 1) for all subjects with available samples, the variants at baseline at signature resistance-associated amino acid positions relative to the appropriate prototypic reference sequences; and 2) for subjects who do not achieve SVR₁₂, post-baseline variants relative to baselines in available samples.

Statistical Methods:
 
Efficacy: The primary efficacy endpoint is the percentage of subjects who achieve SVR₁₂ (HCV RNA < LLOQ 12 weeks after the last actual dose of study drug) within each genotype (GT5 and GT6 subjects) separately across treatment arms. The primary endpoint will be analyzed based on intention to treat (ITT) population. The number and percentage of subjects achieving SVR₁₂ will be summarized with a two-sided 95% confidence interval based on the normal approximation of the binomial distribution unless the rate for SVR₁₂ is 100%, where the Wilson's score method will be used to calculate the confidence interval.
 
The secondary efficacy endpoints within each genotype (GT5 and GT6 subjects) separately, across treatment arms are:
 
 • The percentage of subjects with on-treatment HCV virologic failure. • The percentage of subjects with post-treatment HCV virologic relapse. 
For on-treatment virologic failure and post-treatment relapse, the number and percentage of subjects will be summarized along with a two-sided 95% confidence interval using Wilson's score method. Analyses of additional efficacy endpoints and efficacy subgroup analyses will be performed.

Statistical Methods (Continued):

PROs:

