8.0 Statistical Methods and Determination of Sample Size

8.1 Statistical and Analytical Plans

The primary analysis will occur after all subjects have completed the PT Week 12 Visit or prematurely discontinued treatment. The data for the primary analysis will be locked after data cleaning. Data after PT Week 12 will be added to a new version of the database which will be cleaned and locked at the end of the study.

SAS[®] (SAS Institute, Inc., Cary, NC) for the UNIX operating system will be used for all analyses. All confidence intervals will be two-sided with an alpha level of 0.05.

Descriptive statistics will be provided, such as the number of observations (N), mean, and standard deviation (SD) for continuous variables and counts and percentages for discrete variables.

Safety, and demographic analyses will be performed on all subjects who receive at least one dose of study drug.

Efficacy analyses will be performed on the intention-to-treat (ITT) population defined as all enrolled subjects who receive at least one dose of study drug, unless otherwise specified.

Sensitivity analyses of the primary efficacy endpoint, when applicable, will be performed on the intention-to-treat population modified to exclude subjects not of GT5, 6 according to phylogenetic analyses (mITT-GT), and on the mITT-GT population further modified to exclude subjects who did not achieve SVR₁₂ for reasons other than virologic failure (mITT-GT-VF).

No data will be imputed for any efficacy or safety analysis except for analyses of SVR endpoints (HCV RNA data). HCV RNA values will be selected for the analyses of all SVR endpoints (e.g., SVR₄, SVR₁₂, and SVR₂₄) based on defined visit windows. A backward imputation method will be used to impute missing responses for SVR analyses.

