8.1.2.1 Primary Efficacy Endpoints

The primary efficacy endpoint is the percentage of subjects in who achieve SVR₁₂ (HCV RNA < LLOQ 12 weeks after the last actual dose of study drug) within each genotype (GT5 and GT6 subjects) across the treatment arms. The primary endpoint will be analyzed based on ITT population. The number and percentage of subjects achieving SVR₁₂ will be summarized along with a two-sided 95% confidence interval using the

normal approximation to the binomial distribution, unless the number of SVR₁₂ non-responders is less than 5, where the Wilson's score method will be used for the confidence interval instead.

A summary of reason for SVR₁₂ non-response (e.g., on-treatment virologic failure, relapse, other) will be provided.

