8.2 Determination of Sample Size

It is anticipated that approximately a total of 80 HCV infected patients, (~30 GT5-infected subjects and ~50 GT6-infected subjects) will be enrolled in the study. A minimum of 15 GT5 and 30 GT6 subjects will be enrolled and up to approximately 16 subjects with compensated cirrhosis (regardless of GT) will be enrolled. No formal hypothesis is being tested. If the observed SVR_{12} rate in this study is 97% among 30 GT5 subjects and 50 GT6 subjects, then the half-width of 2-sided 95% normal approximation intervals are 0.061 and 0.047 for the GT5 and GT6 subjects, respectively.

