3.0 Introduction

This statistical analysis plan (SAP) describes the statistical analyses to be completed by the AbbVie Statistics and Statistical Programming Departments for glecaprevir (GLE)/pibrentasvir (PIB) study Protocol M16-126. Study M16-126 evaluates the efficacy and safety of GLE/PIB in HCV treatment-naïve or treatment-experienced (i.e., has failed prior interferon [IFN] or pegylated-IFN [pegIFN] with or without ribavirin [RBV], or sofosbuvir [SOF] plus RBV with or without pegIFN therapy), chronic hepatitis C virus (HCV) genotype (GT) 5 or 6-infected subjects, without cirrhosis for an 8-week treatment duration or with compensated cirrhosis for a 12-week treatment duration.

This SAP (Version 1.0) provides details to further elaborate the statistical methods outlined in Clinical Study Protocol M16-126 incorporating Amendment 1 dated 28 July 2017, and describes analysis conventions to guide the statistical programming. Unless noted otherwise, all analyses will be performed using SAS[®] Version 9.4 (SAS Institute Inc., Carry, NC 27513) or later under the Unix operating system.

The SAP will not be updated in the case of future administrative or minor amendments to the protocol unless the changes have any impact on the analysis of study data.

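### The primary SVR12 interval switches from Wilson to the normal approximation at the fifth non-responder, so at n=50 one more failure raises both limits; the protocol synopsis and 8.2 still follow the earlier rule

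*SAP*

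**What the plan says.** **Operative rule.** SAP 10.3 specifies a "two-sided 95% CI using the normal approximation to the binomial distribution, unless the number of SVR₁₂ non-responders is less than 5", in which case Wilson replaces it. Protocol 8.1.2.1 has the same threshold: "normal approximation to the binomial distribution, unless the number of SVR₁₂ non-responders is less than 5, where the Wilson's score method will be used". The rule is applied to GT5 and GT6 separately in the ITT population. Protocol 8.1 sets the level: "All confidence intervals will be two-sided with an alpha level of 0.05".

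**Origin.** Protocol 1.1 explains that a regulatory authority asked for Wilson when SVR12 rates are high but below 100%, and that the threshold of 5 was adopted in response.

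**Synopsis.** Protocol 1.2 states a different condition, the normal approximation "unless the rate for SVR₁₂ is 100%, where the Wilson's score method will be used to calculate the confidence interval". This is current text, marked "Date of Protocol Synopsis: 28 July 2017". The SAP describes itself as "incorporating Amendment 1 dated 28 July 2017", the same date. Appendix E lists the change to 8.1.2.1 and shows the synopsis condition as the text it replaced there, but the extracted list shows no matching change to the synopsis.

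**Sample size.** Protocol 8.2 gives, at an observed rate of 97%, a "half-width of 2-sided 95% normal approximation intervals are 0.061 and 0.047 for the GT5 and GT6 subjects". SAP 4.3 instead gives expected Wilson intervals of 84.2–99.3% (GT5, n=30) and 88.2–99.1% (GT6, n=50), and says Wilson is the method expected to apply. SAP 12.1 item 1 attributes the new figures to the changed rule.

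**Sensitivity intervals.** Protocol 8.1.2.3 adds a Wilson interval for the ITT primary endpoint without condition. SAP 10.5 reports whichever of the two methods was not used as primary.

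**Elsewhere.** Wilson applies at any count for the secondary endpoints (protocol 8.1.2.2, SAP 10.4), the additional endpoints (protocol 8.1.2.5, SAP 10.7) and, given at least 10 subjects, the subgroups (SAP 10.6).

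**The concern.** Near 100% the Wilson interval is pulled towards 50%, while the normal-approximation interval stays centred on the observed rate. Changing from one to the other at a fixed failure count therefore shifts the interval upward at the moment the result gets worse. If the shift exceeds the fall in the estimate, a group with five failures is reported with better limits than the same group with four. With no hypothesis test, the primary interval is the main inferential output, so this matters for how the result reads.

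The synopsis raises a separate matter. It differs from the body whenever there are 1 to 4 failures, which is the likeliest result at the planning rate, and it can give an upper limit above 100%. Protocol 8.2 describes the study's precision by a method that the protocol's own rule would not use at that rate.

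**Working it through.** **Inputs.** Two-sided 95%, z = 1.960, z² = 3.8415 (protocol 8.1); n = 30 and 50, with minimum enrolment 15 and 30, and a rate of 97% (protocol 8.2).

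**Formulas**, with p the observed rate:
- Normal approximation: p ± z√(p(1−p)/n)
- Wilson: centre (p + z²/2n)/(1 + z²/n); half-width [z/(1 + z²/n)]·√(p(1−p)/n + z²/4n²)

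**1. The plan's own figures.** 1.960 × √(0.97×0.03/30) = 0.0610 and 1.960 × √(0.97×0.03/50) = 0.0473, matching protocol 8.2. Averaging the Wilson limits exactly over a binomial with rate 97% gives 84.1–99.2% at n=30 and 88.2–99.1% at n=50. These are within 0.1 point of SAP 4.3, which used 1000 simulated samples.

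**2. The switch at n=50.**
- 46/50, Wilson: centre (0.92 + 0.0384)/1.0768 = 0.8900; half-width 1.8201 × √(0.001472 + 0.000384) = 0.0784; limits 81.16–96.85%.
- 45/50, normal approximation: 0.90 ± 1.960 × √(0.90×0.10/50) = 0.90 ± 0.0831; limits 81.68–98.32%.

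The estimate falls 2 points, while the lower limit rises 0.52 and the upper 1.47.

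**3. Both planned sizes.**

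| Group | 4 failures, primary (Wilson) | 5 failures, primary (normal) | 5 failures, Wilson |
|---|---|---|---|
| GT6, n=50 | 81.16–96.85% | 81.68–98.32% | 78.64–95.65% |
| GT5, n=30 | 70.32–94.69% | 70.00–96.67% | 66.44–92.66% |

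With Wilson throughout, both limits fall at the fifth failure in both groups.

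**4. Range of n.** Over n = 6 to 299, both limits rise at the switch for every n from 34 up. From n = 12 to 33 only the upper limit rises.

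**5. Chance of reaching the switch.** Binomial P(5 or more failures):

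| True SVR12 rate | n=50 | n=30 |
|---|---|---|
| 97% | 1.7% | 0.2% |
| 95% | 10.4% | 1.6% |
| 90% | 56.9% | 17.6% |

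Only 97% is the plan's value; the other rates are assumptions to show the range.

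**6. Synopsis against body.** The rules differ at 1 to 4 failures. At 97% this has probability 1 − 0.218 − 0.017 = 77% for n=50 and 1 − 0.401 − 0.002 = 60% for n=30. At 29/30 the synopsis rule gives 0.9667 ± 0.0642, or 90.2–103.1%; the body rule gives 83.3–99.4%.

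**7. Protocol 8.2 against 8.1.2.1.** At 97%, 0.03×30 = 0.9 and 0.03×50 = 1.5 failures are expected, so 8.1.2.1 would call for Wilson and not for the method behind 0.061 and 0.047.

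**8. Coverage.** The switching rule covers no less often than Wilson at the seven true rates checked between 85% and 98%. At 90%, 95% and 97%, switching rule against Wilson: n=50, 98.5/97.0, 99.7/96.2 and 95.3/93.7%; n=30, 99.2/97.4, 95.2/93.9 and 94.0/94.0%.

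**The case against.** The case for leaving the rule alone is substantial.

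- **Wilson is reported anyway.** Under protocol 8.1.2.3 and SAP 10.5, a 45/50 result would show 78.6–95.7% beside 81.7–98.3%. This stands, and it reduces the matter to which interval is called primary.
- **The rule is fixed in advance.** A reader might infer that the method is picked once the failures are known, or that two stated rules leave the sponsor free to choose. The documents do not support that. The rule is deterministic, protocol 8.1.2.1 and SAP 10.3 agree, and protocol 1.1 gives its regulatory origin. The synopsis sentence reads as a leftover.
- **Coverage is not the problem.** A reader might infer that the switching rule under-covers. At the rates checked it did not.
- **The reversal is not general.** Both limits rise only from n=34. At the planned GT5 size the lower limit falls slightly, and GT6 may enrol as few as 30.
- **Reaching five is unlikely at 97%.** Missing SVR12 data do count as failures, but only after backward imputation and local-laboratory values have been tried (SAP 6.3).
- **The SAP has dealt with protocol 8.2.** SAP 4.3 gives Wilson limits and SAP 12.1 logs the reason. Protocol 8.2 also labels its figures openly as normal-approximation half-widths.

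All of this limits the consequence. It does not make the interval labelled primary coherent at the switch, and it does not remove the contradiction inside the protocol. Protocol 1.1 gives no reason for keeping the normal approximation at 5 or more failures.

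**Conclusion.** The point holds, at modest size. At n=50 the primary interval improves at both ends when a fifth failure is added, by 0.5 and 1.5 points, and lies about 3 points above Wilson for the same data (lower limit 81.7% against 78.6%, upper 98.3% against 95.7%). At n=30 the reversal affects only the upper limit, by 2.0 points. This rests on the planned group sizes, the uncorrected Wilson formula (consistent with SAP 4.3) and independent binomial outcomes. No test or success threshold depends on it, and at the planned 97% the switch is rarely reached.

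The synopsis conflict is more likely to touch the expected result (77% for GT6 and 60% for GT5 at 97%), but its remedy is textual because the protocol body and the SAP agree. The protocol 8.2 half-widths are correct arithmetic for a method the current rule would not use at that rate.

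**What to change.** 1. In the protocol synopsis, protocol 8.1.2.1 and SAP 10.3, state one rule: the primary 95% interval for SVR12 in each genotype is the Wilson score interval, whatever the number of non-responders.
2. In protocol 8.1.2.3 and SAP 10.5, make the normal approximation the sensitivity interval for the ITT primary endpoint, without a condition on the count.
3. In protocol 8.2, replace 0.061 and 0.047 with the SAP 4.3 limits, 84.2–99.3% for GT5 and 88.2–99.1% for GT6, and drop the sentence in SAP 4.3 that ties the choice of method to the number of non-responders.

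The cost is wording; both intervals are already planned, so nothing new has to be programmed. The stated precision becomes slightly less favourable: half the Wilson width is (99.3 − 84.2)/2 = 7.6 points against 6.1 for GT5, and (99.1 − 88.2)/2 = 5.5 against 4.7 for GT6. With five or more failures, the primary limits will also be lower than under the present rule.

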10.4 Secondary Efficacy Analyses

The secondary efficacy endpoints are:

- The percentage of subjects with on-treatment virologic failure;
- The percentage of subjects with Relapse₁₂.

The number and percentage of subjects with on-treatment virologic failure and Relapse₁₂ in the ITT population will be summarized along with two-sided 95% Wilson score CIs by GT (GT5 and GT6) across treatment arms.

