8.1.2.2 Secondary Efficacy Endpoints

The secondary efficacy endpoints within each genotype (GT5 and GT6 subjects) separately, across treatment arms are:

- The percentage of subjects with HCV on-treatment virologic failure;
- The percentage of subjects with post-treatment HCV virologic relapse. Subjects with reinfection based on HCV NGS will be summarized separately from relapse.

The secondary endpoints of HCV on-treatment virologic failure and post-treatment HCV virologic relapse will be analyzed within each genotype (GT5 and GT6 subjects) separately, across the treatment arms.

For the analysis of post-treatment HCV virologic relapse, completion of treatment is defined as any subject with study drug duration of 52 days and 77 days or greater for subjects allocated to treatment durations of 8 weeks and 12 weeks, respectively.

For on-treatment virologic failure and post-treatment relapse, the number and percentage of subjects will be summarized along with a two-sided 95% confidence interval using Wilson's score method.

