5.0 Analysis Populations

5.1 Definitions for Analysis Populations

5.1.1 Intention-to-Treat (ITT) Population

All enrolled subjects who receive at least one dose of study drug will be included in the ITT population. Demographic, baseline characteristics, exposure, compliance, concomitant medication and medical history analyses will be performed on the ITT population overall and according to the treatment arm assignment, i.e., subject grouping will be based on the arm to which the subject was assigned. Demographic and baseline characteristics will also be summarized by GT. Efficacy analyses will be performed by GT (GT5 and GT6) and for the overall ITT population.

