SVR₄ = HCV RNA $<$ LLOQ in the SVR₄ window (4 weeks after the last actual dose of study drug) without any confirmed quantifiable (\geq LLOQ) post-treatment value before or during that SVR window.

SVR₁₂ = HCV RNA $<$ LLOQ in the SVR₁₂ window (12 weeks after the last actual dose of study drug) without any confirmed quantifiable (\geq LLOQ) post-treatment value before or during that SVR window.

SVR₂₄ = HCV RNA $<$ LLOQ in the SVR₂₄ window (24 weeks after the last actual dose of study drug) without any confirmed quantifiable (\geq LLOQ) post-treatment value before or during that SVR window.

Relapse₁₂ = confirmed HCV RNA \geq LLOQ between end of treatment and 12 weeks after last actual dose of study drug (up to and including the SVR₁₂ window) for a subject with HCV RNA $<$ LLOQ at Final Treatment Visit who completed treatment, excluding reinfection as described below.

Relapse₂₄ = confirmed HCV RNA \geq LLOQ within the SVR₂₄ window for a subject who achieved SVR₁₂ and has HCV RNA data available in the SVR₂₄ window, excluding reinfection.

Relapse_{overall} = confirmed HCV RNA \geq LLOQ between end of treatment and up to and including the last HCV RNA measurement collected in the Post-Treatment Period for a subject with HCV RNA $<$ LLOQ at Final Treatment Visit who completed treatment, excluding reinfection.

Virologic failure for SVR₁₂ = On-treatment virologic failure or Relapse₁₂.

Only subjects who have at least one post-treatment HCV RNA value will be included in analyses of relapse. For the analysis of relapse, completion of treatment is defined as any subject with study drug duration of 52 days or greater for Arm A, and 77 days or greater for Arm B. If the last available post-treatment value is \geq LLOQ, then the subject will be considered a relapse (i.e., will not require confirmation).

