10.7 Additional Efficacy Analyses

As additional analyses, the analyses of SVR₁₂ (as described in Section 10.3) and on-treatment virologic failure and Relapse₁₂ (as described in Section 10.4) in the ITT population and the sensitivity analyses of SVR₁₂ in the mITT-GT and mITT-GT-VF populations (as described in Section 10.5) will be performed for the overall population

across treatment arms and genotypes. For the SVR₁₂ endpoints, two-sided 95% CIs using both the normal approximation to the binomial distribution and the Wilson's score method will be calculated. For the other endpoints, only the two-sided 95% CI using Wilson's score method will be calculated.

The following additional efficacy endpoints will be summarized and analyzed for the ITT population, by GT (GT5 and GT6) across treatment arms and overall:

- The percentage of subjects with HCV RNA < LLOQ at each post-baseline visit in the Treatment Period (using data as observed);
- The percentage of subjects with SVR₄;
- The percentage of subjects with SVR₂₄;
- The percentage of subjects who relapsed after achieving SVR₁₂ (**Relapse₂₄**).
- The percentage of subjects with virologic failure through Post-Treatment Week 12 (i.e., the SVR₁₂ non-responders due to **on-treatment virologic failure** or **Relapse₁₂**)

For each of the above endpoints, a two-sided 95% CI using Wilson's score method will be calculated along with the number and percentage of subjects. Imputations for missing data will be performed as described in Section 6.3 for all the additional endpoints listed above except the first one.

For the overall ITT population and by GT, a summary of the subjects who completed treatment and relapsed (defined as **Relapse_{overall}**) will be prepared displaying the number and percentage of subjects relapsing overall and by the SVR visit window where the first relapse occurred (within the SVR₄, SVR₁₂, SVR₂₄ windows or after SVR₂₄ window), including the subject number and the SVR visit window corresponding to the first occurrence of relapse. A similar summary will be prepared for subjects who prematurely discontinued treatment and relapsed after having HCV RNA < LLOQ at their Final Treatment Visit.

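### The Relapse12 rate has two conflicting stated denominators, and neither is the at-risk set in the Relapse12 definition

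*SAP*

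**What the plan says.** - **SAP 10.4** names two secondary endpoints, on-treatment virologic failure and Relapse12. Their counts and percentages "in the ITT population will be summarized along with two-sided 95% Wilson score CIs by GT (GT5 and GT6) across treatment arms". SAP 10.7 repeats both on the ITT population for all genotypes and arms together.
- **SAP 5.1.1** defines that population: "All enrolled subjects who receive at least one dose of study drug will be included in the ITT population".
- **SAP 10.1** has a narrower rule: "Only subjects who have at least one post-treatment HCV RNA value will be included in analyses of relapse".
- **SAP 10.1** also defines the event. Relapse12 is confirmed quantifiable HCV RNA, up to and including the SVR12 window, in a subject below "LLOQ at Final Treatment Visit who completed treatment, excluding reinfection as described below". Completion means "study drug duration of 52 days or greater for Arm A, and 77 days or greater for Arm B".
- **Protocol 8.1.2.2** has the same completion rule, with the two day counts as minimums for the 8-week and 12-week durations, but names no denominator: "For the analysis of post-treatment HCV virologic relapse, completion of treatment is defined as any subject with study drug duration of 52 days and 77".
- **SAP 10.7** covers rebound after an early stop separately: "A similar summary will be prepared for subjects who prematurely discontinued treatment and relapsed after having HCV RNA" below LLOQ at the Final Treatment Visit.

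**The concern.** A dosed subject with no post-treatment sample belongs to the 10.4 denominator but not to the 10.1 denominator, so the two rules can give different percentages from the same data.

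Both sets can also hold subjects who cannot be a Relapse12: those who stopped before day 52 or 77, and those still quantifiable at the Final Treatment Visit. Take a subject who stops early while suppressed, then rebounds and has post-treatment samples. Under either stated rule, that subject is a non-event in the relapse rate.

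Relapse12 is one of only two secondary efficacy endpoints, and the SAP is meant to guide programming. Two programmers could follow it faithfully and report different n/N. Where the wider denominator matters, it favours the drug.

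**Working it through.** **1. Who is in each set**

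| Subject | ITT (10.4, 10.7) | Post-treatment value (10.1) | Can be a Relapse12 |
|---|---|---|---|
| Completed, below LLOQ at Final Treatment Visit, has post-treatment value | in | in | yes |
| Same, but no post-treatment value | in | out | no |
| Stopped early, has post-treatment value | in | in | no |
| Quantifiable at Final Treatment Visit, has post-treatment value | in | in | no |

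Two denominators are stated. The third, the at-risk set in the first row, is only implied by the event definition.

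**2. Check of the interval method.** The documents give no precision figure for relapse, so the method was checked on SVR12. The Wilson interval for x events in n, with p = x/n and z = 1.96, is

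[p + z²/(2n) ± z·√(p(1−p)/n + z²/(4n²))] / (1 + z²/n).

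Averaged over Binomial(n, 0.97), it gives (84.1%, 99.2%) for n = 30 and (88.2%, 99.1%) for n = 50. SAP 4.3 states (84.2%, 99.3%) and (88.2%, 99.1%) from 1000 simulated samples, so they agree within 0.1 point. The normal half-widths z·√(0.97×0.03/n) are 0.061 and 0.047, as in Protocol 8.2.

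**3. Effect on relapse.** Inputs are 30 GT5 and 50 GT6 subjects (Protocol 8.2). The number not at risk, k, is an assumption: the documents give no early-stop or missing-sample rate, so the range taken is 0 to 10%. The rate over the at-risk set is the ITT rate times n/(n−k). At 10% the factor is 30/27 = 50/45 = 1.11. At k = 0 the denominators coincide.

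| Group | Relapses | ITT: rate (upper 95% limit) | At-risk set, 10% removed |
|---|---|---|---|
| GT5 | 0 | 0/30 = 0% (11.4%) | 0/27 = 0% (12.5%) |
| GT5 | 1 | 1/30 = 3.3% (16.7%) | 1/27 = 3.7% (18.3%) |
| GT5 | 2 | 2/30 = 6.7% (21.3%) | 2/27 = 7.4% (23.4%) |
| GT6 | 0 | 0/50 = 0% (7.1%) | 0/45 = 0% (7.9%) |
| GT6 | 1 | 1/50 = 2.0% (10.5%) | 1/45 = 2.2% (11.6%) |
| GT6 | 2 | 2/50 = 4.0% (13.5%) | 2/45 = 4.4% (14.8%) |

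With fewer subjects removed the shift is smaller: GT5 1/29 = 3.4% (17.2%) and GT6 1/48 = 2.1% (10.9%). At the GT5 enrolment minimum of 15 with one not at risk (6.7%), 1/15 = 6.7% (29.8%) becomes 1/14 = 7.1% (31.5%).

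For scale, the one-relapse ITT intervals run from 0.6% to 16.7% in GT5 and from 0.4% to 10.5% in GT6, about 16 and 10 points wide.

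**The case against.** **The rules may be layered rather than rival.** SAP 10.1 makes ITT the default unless something else is specified, and then gives specific rules for relapse. On that view, the ITT wording in 10.4 names the source population, as opposed to the mITT sets in 10.5, and 10.1 narrows it. The Relapse24 definition supports this: it asks for HCV RNA data in the SVR24 window, which adds nothing for someone who already has a confirmed quantifiable value there. It does work only as a condition on who is counted. The Relapse12 definition is built the same way, and both documents define completion for the relapse analysis, not only for the event. Under this reading nothing is understated.

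This is plausible and may be what was intended. But the only express inclusion rule is the post-treatment value. No sentence makes completion and suppression conditions on the Relapse12 denominator.

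**A reader might infer that rebounds after an early stop are hidden.** The documents do not support that. Such a rebound, up to the SVR12 window, is a failure in the primary endpoint, is assigned to the premature-discontinuation reason (SAP 10.1), is listed by reason (10.3) and has its own summary (10.7). An at-risk denominator would not turn it into a relapse; it takes the subject out of the rate. Counting it, for example as 2/30 = 6.7% instead of 1/30 = 3.3%, would be a different endpoint.

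**A reader might also infer that the rate is bound to be understated.** That needs the literal reading, at least one subject not at risk and at least one relapse. Zero relapses is a realistic outcome: Protocol 5.6.1 reports SVR12 in all 34 non-cirrhotic GT4 to GT6 subjects treated for 12 weeks. Then the estimate is 0% under every denominator and only the upper limit moves.

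**Conclusion.** The conflict is real and minor. SAP 10.4 and 10.7 state one denominator for Relapse12 and SAP 10.1 another, and neither equals the at-risk set that the definition implies.

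Followed literally, the plan lowers the Wilson upper limit whenever any subject is not at risk, and lowers the rate as well once there is a relapse. At planned enrolment, with an assumed 10% not at risk, one relapse moves the rate by 0.4 points in GT5 and 0.2 in GT6, and the upper limit by 1.6 and 1.1 points. With no relapses the upper limit moves by 1.1 and 0.8 points. These shifts are small against the interval widths.

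The endpoint is descriptive, no hypothesis is tested, and the SVR12 analysis is unaffected. The reason to act is that the reported n/N should follow from the text without a programmer's choice.

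**What to change.** In SAP 10.1, 10.4 and 10.7, state one denominator for Relapse12 and Relapse_overall: ITT subjects who

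- completed treatment (at least 52 days in Arm A, at least 77 days in Arm B),
- had HCV RNA below LLOQ at the Final Treatment Visit, and
- have at least one post-treatment HCV RNA value.

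Keep the full ITT denominator for on-treatment virologic failure. Show n/N for Relapse12 next to the existing 10.7 summary of relapse after early discontinuation, so that subjects outside the rate stay visible.

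This costs a sentence and a denominator flag and needs no new data. The only downside is a relapse figure that may be slightly less favourable.
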